13.1.1.25 CYTOCHROME P450 3A4 (CYP3A4) SUBSTRATES

Interaction Rating = Moderate Be cautious with this combination.

Severity = Moderate • Occurrence = Possible • Level of Evidence = **D**

There's preliminary evidence that feverfew might inhibit cytochrome P450 3A4 (CYP3A4) enzyme (12479,19361). So far, this interaction has not been reported in humans. However, watch for an increase in the levels of drugs metabolized by CYP3A4 in patients taking feverfew. Some drugs metabolized by CYP3A4 include lovastatin (Mevacor), ketoconazole (Nizoral), itraconazole (Sporanox), fexofenadine (Allegra), triazolam (Halcion), and numerous others. Use feverfew cautiously or avoid in patients taking these drugs.

Interactions with Herbs & Supplements

ANTICOAGULANT/ANTIPLATELET HERBS AND SUPPLEMENTS: Some evidence suggests that feverfew may inhibit platelet aggregation. However, this has not been demonstrated in humans (6935,6936,6942,6943,6944,6945,6951). Theoretically, concomitant use of feverfew and herbs that affect platelet aggregation could increase the risk of bleeding in some people. Some of these herbs include angelica, clove, danshen, garlic, ginger, ginkgo, Panax ginseng, horse chestnut, red clover, turmeric, and others.

SKULLCAP

There are no Serious Drug Interactions known for Skullcap. There is one moderate interaction of anecdotal evidence that Skullcap may cause sedation, so there should be caution as there may be additive effects of the use with CNS deressants.

13.1.1.26 CNS DEPRESSANTS

Interaction Rating = **Moderate** Be cautious with this combination. Severity = High • Occurrence = Possible • Level of Evidence = **D**

Animal research and clinical evidence suggests that skullcap might cause sedation and cognitive impairment (12216,74008). Theoretically, concomitant use of skullcap and drugs with sedative and anesthetic properties may cause additive therapeutic and adverse effects. Some CNS depressants are benzodiazepines, pentobarbital (Nembutal), phenobarbital (Luminal), secobarbital (Seconal), thiopental (Pentothal), fentanyl (Duragesic, Sublimaze), morphine, propofol (Diprivan), and others.

Interactions with Herbs & Supplements

HERBS AND SUPPLEMENTS WITH SEDATIVE PROPERTIES: Skullcap might cause sedation and cognitive impairment (12216,74008). Theoretically, concomitant use of skullcap with herbs that have sedative properties might enhance the therapeutic and adverse effects. Some of these supplements include 5-HTP, calamus, California poppy, catnip, hops, Jamaican dogwood, kava, St. John's wort, valerian, yerba mansa, and others.

plodəsuod gnib	ouloni seitivitise ylisb le	nsu ob ot yżilids ir ities?	sadaches limit you ool, or social activ	How often do ho work, work, scho			
syswIA	Very Often	Sometimes	Кагеју	Иечег			
	vere?	rəs nisq əht si nətt	neadaches, how o	Муси уои раче			
APACT TES	▲V I			the way you feel an			

Higher scores indicate greater impact on your life.

HIT-61'm (Headache Impact Test"n) © 2000 QualityMetric Incorporated and the GlaxoSmithKline Group of Companies - All rights reserved

HIT-6 $^{\rm TM}$ (Headache Impact Test $^{\rm TM}$) is a trademark of QualityMetric Incorporated and the GlaxoSmithKline Group of Companies

Score range is 36-78.

If You Scored 60 or More

your life, like family, work, school or social activities. are more severe than those of other headache sufferers. Don't let your headaches stop you from enjoying the important things in Your headaches are having a very severe impact on your life. You may be experiencing disabling pain and other symptoms that

Make an appointment today to discuss your HIT-6 results and your headaches with your doctor.

If You Scored 56 – 59

symptoms, causing you to miss some time from family, work, school, or social activities. Your headaches are having a substantial impact on your life. As a result you may be experiencing severe pain and other

Make an appointment today to discuss your HIT-6 results and your headaches with your doctor.

If You Scored 50 – 55

work, school, or social activities. Your headaches seem to be having some impact on your life. Your headaches should not make you miss time from family,

Make sure you discuss your HIT-6 results and your headaches at your next appointment with your doctor.

If You Scored 49 or Less

continue to track how your headaches affect your life. Your headaches seem to be having little to no impact on your life at this time. We encourage you to take HIT-6 monthly to

If Your Score on HIT-6 is 50 or Higher

You should share the results with your doctor. Headaches that are disrupting your life could be migraine.

include medication. bestaches affect the lives of their patients, they are much more likely to provide a successful treatment program, which may Take HIT-6 with you when you visit your doctor because research shows that when doctors understand exactly how badly

HIT is also available on the Internet at www.headachetest.com.

The Internet version allows you to print out a personal report of your results as well as a special detailed version for your d octor.

Don't forget to take HIT-6 again or try the Internet version to continue to monitor your progress.

TIH tuodA

in collaboration with the psychometricians who developed the SF-36 $^{\text{\tiny ®}*}$ health assessment tool. ability to function. HIT was developed by an international team of headache experts from neurology and primary care medicine school, at home and in social situations. Your score shows you the effect that headaches have on normal daily life and your The Headache Impact Test (HIT) is a tool used to measure the impact headaches have on your ability to function on the job, at

provider for advice specific to your situation. HIT is not intended to offer medical advice regarding medical diagnosis or treatment. You should talk to your healthcare

SF-36® is a registered trademark of Medical Outcomes Trust and John E. Ware, Jr.

HIT-6 TM (Headache Impact Test TM) \otimes 2000 QualityMetric Incorporated and the

GlaxoSmithKline Group of Companies - All rights reserved

GlaxoSmithKline Group of Companies HIT-6" (Headache Impact Test") is a trademark of QualityMetric Incorporated and the

13.1.4Appendix D Baseline Form

Baseline

Please answer the following questions to the best of your abilities.

4	_	
1 1	Inmorran	nicc
1.	Demograpi	1111.5
	- ccop.	

- a. Race/Ethnicity (Black or African American, White, Asian, American Indian or Alaska Native, Native Hawaiian or another pacific islander, other: _____, do not want to share)
- b. Sex (M, F, or Do not want to share)
- 2. On average how often do you have headaches? (A few times a year, once a month, A few times a month, once a week, 2-3 times a week, Everyday)
- 3. How do your headaches typically begin? (Gradually, suddenly or Varies)
- 4. How long does it usually take for your headache to reach maximum intensity? (0-30 min, 31 min- 1 hour, +1 hour)
- 5. How long do your Headaches usually last without medication? (30 min-1hour, 1-2 hour, >2 hours, does not resolve)
- 6. On average how bad are your headaches without medication? (1-10)
- 7. What do your headaches usually feel like? (pressure, stabbing, throbbing, Tight band, burning, dull ache)
- 8. Do any of the following bring on or trigger your headaches (check all that apply)?
 - a. Food
 - b. Caffeine (too much/too little)
 - c. Hunger/skipping meals
 - d. Fatigue
 - e. Stress
 - f. Alcohol/wine
 - g. Too much/too little sleep
 - h. Menstruation
 - i. Physical activity
 - j. Prolonged computer work
 - k. Bright light/sun
 - I. Loud sounds
 - m. Other:
 - n. None of the above
- 9. Do you experience any of the following symptoms before your headache begins (check all that apply)?
 - a. Mood/Personality Changes
 - b. Changes in appetite
 - c. Neck pain
 - d. Fatigue

i. Right awayii. Within an hour

iii. 1-2 hours

iv. >2 hours

- d. How long do your headaches usually last with medication? (30 min-1hour, 1-2 hour, >2 hours, does not resolve)
- 14. How many hours of work/school/leisure time do you miss a month because of your headaches? (Free response)

- 2 Minor Annoyance occasional strong twinges. No medication needed.
- **3** Annoying enough to be distracting. Mild painkillers take care of it (Aspirin, Ibuprofen).
- **4** Can be ignored if you are really involved in your work, but still distracting. Mild painkillers remove pain for 3-4 hours.
- **5** Can't be ignored for more than 30 minutes. Mild painkillers ameliorate pain for 3-4 hours.
- **6** Can't be ignored for any length of time, but you can still go to work and participate in social activities. Stronger painkillers (Codeine, narcotics) reduce pain for 3-4 hours.
- **7** Makes it difficult to concentrate, interferes with sleep. You can still function with effort. Stronger painkillers are only partially effective.
- **8** Physical activity severely limited. You can read and converse with effort. Nausea and dizziness set in as factors of pain.
- 9 Unable to speak. Crying out or moaning uncontrollably near delirium.
- 10 Unconscious. Pain makes you pass out.

Pain Scale at 30 minutes

Please rate your pain 30 minutes after taking the test product. Circle your answer.

- 0 Pain Free
- 1 Very minor annoyance occasional minor twinges. No medication needed.
- 2 Minor Annoyance occasional strong twinges. No medication needed.
- **3** Annoying enough to be distracting. Mild painkillers take care of it (Aspirin, Ibuprofen).
- **4** Can be ignored if you are really involved in your work, but still distracting. Mild painkillers remove pain for 3-4 hours.
- **5** Can't be ignored for more than 30 minutes. Mild painkillers ameliorate pain for 3-4 hours.
- **6** Can't be ignored for any length of time, but you can still go to work and participate in social activities. Stronger painkillers (Codeine, narcotics) reduce pain for 3-4 hours.
- **7** Makes it difficult to concentrate, interferes with sleep. You can still function with effort. Stronger painkillers are only partially effective.
- **8** Physical activity severely limited. You can read and converse with effort. Nausea and dizziness set in as factors of pain.
- 9 Unable to speak. Crying out or moaning uncontrollably near delirium.
- 10 Unconscious. Pain makes you pass out.

Pain Scale at 1 hour

Please rate your pain 1 hour after taking the test product. Circle your answer.

- 0 Pain Free
- 1 Very minor annoyance occasional minor twinges. No medication needed.
- 2 Minor Annoyance occasional strong twinges. No medication needed.
- **3** Annoying enough to be distracting. Mild painkillers take care of it (Aspirin, Ibuprofen).
- **4** Can be ignored if you are really involved in your work, but still distracting. Mild painkillers remove pain for 3-4 hours.
- **5** Can't be ignored for more than 30 minutes. Mild painkillers ameliorate pain for 3-4 hours.
- **6** Can't be ignored for any length of time, but you can still go to work and participate in social activities. Stronger painkillers (Codeine, narcotics) reduce pain for 3-4 hours.
- **7** Makes it difficult to concentrate, interferes with sleep. You can still function with effort. Stronger painkillers are only partially effective.
- **8** Physical activity severely limited. You can read and converse with effort. Nausea and dizziness set in as factors of pain.
- 9 Unable to speak. Crying out or moaning uncontrollably near delirium.
- 10 Unconscious. Pain makes you pass out.

	Afte	r your	headache	resolved	please com	plete any	of the	following	questions i	if applicabl
--	------	--------	----------	----------	------------	-----------	--------	-----------	-------------	--------------

Did your symptoms resolve completely with the test product? Yes No If yes, time of complete symptom resolution:						
Did you need to take another medication: Yes No						
Medication #1:	Dose:	Time:				
Medication #2:	Dose:	Time:				
Medication #3:	Dose:	Time:				
Did your symptoms resolve completely with taking your medication? Yes No						
After taking medication, time of complete resolution of symptoms:						
Did you experience any side effects after taking the test product? (Y/N) If yes, Please fill out the Adverse Event form.						

13.1.6Appendix F Study Exit Form

symptoms? (y/n)

Study Exit

1.	Pleas	e rate y	our ov	erall ex	perience w	ith th	e test	produc	t.	
0 Poor	1	2	3	4	5 Neutral	6	7	8	9	10 Excellent
1a	. Why?	(free r	espons	e)						
2.	Do yo	ou feel t	hat th	e test p	roduct help	ed w	ith yo	ur head	aches i)
0 Not at	all	2	3	4	5 Neutral	6	7	8	9	10 definitely
3. How likely are you to recommend the test product to your friends or family members?										
0 Not Li	1 kely	2	3	4	5 Neutral	6	7	8	9	10 Extremely Likely
4. Do you feel that the test product helped your body cope with occasional tension and occasional head discomfort?										
0 Not at	all	2	3	4	5 Neutral	6	7	8	9	10 definitely
5.		=	_		you like to sistency, or				-	xperience with the sponse)

6. Did the test product help prevent you from having to take any other medication for your

13.1.7Appendix G Adverse Event Form

Tension AE document

- 1. Did you experience any side effects after taking the test product? Y/N
 - a. If so, did you experience any of the following
 - o itching, rash, hives, throat/lip/tongue swelling, wheezing
 - low blood pressure, fainting, chest pain, shortness of breath, palpitations, irregular heart beat
 - o severe, persistent nausea, vomiting, diarrhea, or abdominal pain
 - o difficulty urinating, decreased urination
 - o fatigue, appetite loss, yellowing skin/eyes, itching, dark urine
 - severe joint/muscle pain
 - o slurred speech, one-sided weakness of face, arm, leg, vision
 - o abnormal bleeding from nose or gums
 - o blood in urine, stool, vomit,
 - o marked mood, cognitive, or behavioral changes, thoughts of suicide
 - o Other:
- 2. Please give a description of the event
- 3. How soon after taking the test product did you experience the side effect?
- 4. What did you do to alleviate the side effect?
- 5. Did you have to go to the hospital or see a doctor for this side effect?
 - a. Please describe any diagnosis or treatment that they provided.
 - b. If you were seen in the hospital, please upload any discharge paperwork or other documents from the hospital.

13.1.8Appendix H Test Product Insert

Welcome to the Tension Headache Relief Trial!

We appreciate you taking the time to participate in this trial. As you may already know, the aim of this study is to measure the impact the test product has on your headache symptoms. Please take the time to read the following information below to become acquainted with the trial instructions.

Instructions upon Study Product Receipt:

- 1. Please log onto the study portal and acknowledge the receipt by completing the 'Start Form'
- 2. Enclosed in the study bag, please find a 3-episode supply of the tension relief test product.
- 3. You will take the test product the next time you have a headache and need to take something to relieve the discomfort.

Instructions Once Product Intake Begins:

- 1. The next time you have a headache and feel the need to take the test product, you will FIRST start the headache diary (paper forms included in this package).
 - You will complete the date of the episode, the time the episode began, what triggered the headache, type/description of the pain, its location, and record other symptoms (if applicable).
 - REMINDER: DO NOT TAKE ANY OTHER MEDICATION/SUPPLEMENT DURING THE HOUR AFTER TAKE THE TEST PRODUCT.

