- After completing the surveys, the participant will take test product. The participant will take 2 capsules with 6-8 oz. of water per headache episode. With a max of 6 pills per day. (If participant takes 6 pills in 1 day this will be defined as 3 headache episodes and the patient will be exited from the study).
- After taking the test product, the participant will complete a Mankoski pain scale at 15 minutes, 30 minutes, and 1 hour after taking the test product.
- Once the participant's symptoms resolve, the participant will complete the headache diary.
- If the participant takes any other medication outside of the test product, the participant will record this on the headache diary.
- After taking the test product, the participant will be instructed to fill out an Adverse Event form for any side-effects experienced.
- After the first headache episode, the participant will be asked to complete the same process for another 2 headache episodes; however, these are not required.
- If the participant completes the required assessments for a total of 3 headache episodes, they will be prompted, by email, to exit the study.

- If the participant only completes the required assessments for the required 1 headache episode, the participant will be prompted, by email, to complete the study exit form and will be exited from the study on day 60 (60 days from the day of receipt of the test product).
- The sponsor nor Hawthorne Effect Inc. will not make any attempt to collect any unused product.
- Upon receipt of study exit survey and review of completed study forms, participant will receive an Amazon gift card of \$25 via email.

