- Present intention is that the analysis will be performed in R, and the precise form of algorithms will be the default of R. Kaplan-Meier, log-rank, and proportional hazards algorithms will be the defaults of the survival package. [13]
- The exact items to be compared depend on what is reported in each historical control study. When possible, the items will include symptom relief at each time measured, including within-patient p-values, and time to the lowest level on a 4-point scale and to

the lowest 2 levels on a 10-point scale. as well as reported baseline characteristics. When two-arm studies are compared, both arms will be reported in this comparison. Specific studies to be considered will be identified prior to the analysis of actual trial data.

8 Informed Consent Process

The study protocol and informed consent will be reviewed approved by Advarra Institutional Review Board, prior to study start.

Study candidates will learn about the study via digital advertisements. If interested in learning more, they will be referred to a website "landing page" that will provide detailed information about the study. They may opt to complete a screening survey ascertaining study eligibility through patient reported outcomes. If successfully completed (no exclusion criteria are selected), candidate will be invited to review the study consent form tutorial which includes the opportunity to ask questions related to the study from the Principal Investigator or delegated authority of the investigator. Candidate will be provided with contact information to reach investigator or study manager as desired.

Candidate may sign the informed consent via electronic signature as provided by Hawthorne Effect. The study manager will verify candidate signature prior to enrollment as a study participant.

9 Subject Confidentiality

All participants' data and personal information will be kept confidential. Only those involved with the study will have access to participant information. The data will be stored by Hawthorne Effect on a HIPAA compliant platform. The platform, which the data is stored on, will require a personalized username and password to gain access.

10 Publication

Prior to the first patient enrolled, study will be registered on clinicaltrials.gov and submit the results for advertisement and promotion purposes.

11 Limitations

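### For a headache that ends after the first hour without other medication, the diary records an end time only if the participant credits the test product

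*Combined protocol and SAP*

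**What the plan says.** Appendix E takes Mankoski ratings before intake and at 15, 30 and 60 minutes, with 0 meaning no pain. The last is introduced by "Please rate your pain 1 hour after taking the test product. Circle your answer". A closing block follows, which participants are told to fill in once the headache has resolved, as far as it applies. It asks:

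- about the product: "Did your symptoms resolve completely with the test product? Yes No If yes, time of complete symptom resolution";
- about anything else taken: "Did you need to take another medication: Yes No", with lines for name, dose and time;
- about the result of that other treatment: "Did your symptoms resolve completely with taking your medication? Yes No";
- and, for its end time: "After taking medication, time of complete resolution of symptoms".

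Section 6.1 says "Once the participant's symptoms resolve, the participant will complete the headache diary". The schedule in section 6.2 marks the diary at the event and at 60 minutes.

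The baseline form (Appendix D) asks how long headaches usually last, with and without medication. It does not ask for a cause, and it has a separate category for headaches that do not go away. Section 7.1 plans a paired t-test against normal behavior without naming the variable. Section 7.3 plans a presentation beside published studies that includes, where possible, "time to the lowest level on a 4-point scale" and the time to the two lowest levels of a 10-point scale.

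**The concern.** Whether and when a headache ended is a fact. What ended it is a judgement, and here an unblinded one in a study without a control group. Both resolution items in the diary ask for the two together, and the end-time fields depend on the answer. Two participants with the same course, say a headache that fades after two hours with nothing else taken, can leave different records. One credits the product and supplies a time. The other does not, and leaves no time.

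At stake is any statement about how many headaches ended after the first hour and how long they lasted. Resolution by the diary would be resolution as credited to the product, and the recorded times would come from a subset selected by that opinion. A missing end time cannot be recovered once the diaries are in.

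**Working it through.** **The plan's own figure.** Section 7.2 gives 68 patients for 90% power, with mean improvement 2 and SD 5, by paired t-test. Significance level and sidedness are not stated there; I assume two-sided 0.05. The noncentrality is (2/5) × √68 = 3.30 on 67 degrees of freedom, which gives power 0.902, and 68 is the smallest n reaching 0.90. The figure reproduces. It rests on the Mankoski ratings alone, so nothing below changes it.

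**Paths through the diary.**

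| True course | Product item | Other medication | End time |
|---|---|---|---|
| Ended within 60 min, nothing else taken | Yes or No | No | Only if Yes, but a rating of 0 places the ending within 0–15, 15–30 or 30–60 min |
| Ended after 60 min, nothing else taken, product credited | Yes | No | Recorded |
| Ended after 60 min, nothing else taken, product not credited | No | No | None |
| Not ended, nothing else taken | No | No | None |
| Ended after other medication | Normally No | Yes | Recorded in the second time field |

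Rows three and four leave the same entries. The block's lead-in suggests that a completed block means an ended headache, but this helps only in part. The items allow No, the as-applicable wording makes blanks ambiguous, and the schedule in section 6.2 places the diary at 60 minutes, when No may mean not yet. Even if the lead-in is trusted, row three has no time.

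**Illustration of size.** The 97 treated participants come from section 5.1, counted here as one headache each. The rest are assumptions, because the documents give no such rates:

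- *u*, the share ending after 60 minutes with nothing else taken: 10% to 30%;
- *a*, the share of those answering Yes: 0 to 100%;
- *v*, the share not ended and with nothing else taken: 5% to 10%.

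Formulas and results:

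- Late endings credited to the product = 97 × u × a. The range is 0 to 97 × 0.30 = 29.1.
- Late endings left as No/No without a time = 97 × u × (1 − a). The range is 0 to 29.1. With u = 10% and a = 0 it is 9.7.
- Share of No/No records that had in truth ended = u(1 − a) / [u(1 − a) + v]. It is 0 when a = 1. It is 0.10/0.20 = 50% when u = 10%, a = 0 and v = 10%. It is 0.30/0.35 = 86% when u = 30%, a = 0 and v = 5%.

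For a fixed true course, the recorded share of late resolution can therefore lie anywhere from 0 to u, depending only on how participants attribute it.

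**The case against.** The strongest reply is that no named endpoint uses these items. The primary endpoint is the change in Mankoski rating, and neither the proportion resolved nor the time to complete resolution is listed as a secondary endpoint. That stands. Time to other intervention draws its event times from the medication lines. All that is lost there is knowing which event-free headaches had already ended.

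A reader might infer that resolution cannot be computed from the diary at all. The documents do not support that: every participant is asked for a rating at 15, 30 and 60 minutes, so pain-free status at those times, and the interval in which pain stopped, are available without attribution. The loss is confined to later endings and to exact times.

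A reader might also infer that the literature presentation fails as a whole. It does not. Its time outcomes are defined on scale levels, the ratings supply them up to 60 minutes, and no formal comparison is planned. Only the part beyond 60 minutes is touched.

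A lay participant may read the first question as meaning that only the product was taken, and answer Yes with a time. That is possible, and it would reduce the missing times. But the form does not say which reading is meant, and such a Yes would still be recorded as resolution with the product.

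Finally, one might extend the point to exit item 6, on whether the product spared other medication. The exit form is there to collect opinion, and the diary asks separately about other medication, so no change is needed there.

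**Conclusion.** The point holds within limits. For headaches that end after 60 minutes without other medication, the end time is recorded only when the participant credits the product. The remaining records cannot be reliably told from headaches that had not ended.

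The affected outputs are descriptive summaries of resolution and duration, a comparison with normal behavior if duration is the variable chosen, and time to low pain beyond 60 minutes in the literature presentation. The baseline form asks about duration neutrally, and the diary has no neutral counterpart after the first hour.

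The size cannot be fixed from the documents. The range of 0 to 29 missing end times per 97 treated headaches rests wholly on the assumed rates. With up to three episodes per participant the count could be larger.

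One further inference should be resisted: that neutral wording would show whether the product works. Without a control group, a headache that ended because of the product and one that ended by itself look the same under any wording. Section 11 already states that there is no concurrent control.

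**What to change.** In Appendix E, replace the two attribution items with two factual ones:

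1. *Has your headache gone completely? Yes/No. If yes, the date and time it ended.* Ask this of everyone, for every treated headache.
2. *Did you take any other medication before it ended? Yes/No. If yes, name, dose and time.*

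Derive resolution with and without other medication from these answers, and report it without attributing it to the product. A No to the first item then marks a headache still open when the item was answered. Opinion about the product remains available from the exit form.

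The cost is a rewording of the closing diary block in the portal and on paper. It adds no visits or participants and changes no sample size. It has to be done before diaries are collected.

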6.2 Study Schedule of activities

Assessments	Screening	Consent	Before Receipt of Test Product	Product Received	Event 1	15 Minutes After Event Start	30 Minutes After Event Start	60 Minutes After Event Start
Study Window								
Screening Survey	Х							
Consent		X						
Baseline Survey			Х					
Demographics			Х					
Medications & Supplements			Х					
Acknowledgement of receipt of test product				X				
Headache Diary					X			X
10-point Mankoski Scale					Х	Х	Х	Х
Test Product Consumed					Х			
AE Assessment					X	X	X	X
Study Exit Survey								

Assessments	Event 2	15 Minutes After Event Start	30 Minutes After Event Start	60 Minutes After Event Start	Event 3	15 Minutes After Event Start	30 Minutes After Event Start	60 Minutes After Event Start	Study Exit
Study Window									
Screening Survey									
Consent									
Baseline Survey									
Demographics									
Medications & Supplements									
Acknowledgement of receipt of test product									
Headache Diary	Х			X	Х			X	
10-point Mankoski Scale	X	X	Х	X	X	X	X	X	
Test Product Consumed	Х				X				
AE Assessment	Х	X	Х	X	X	X	Х	X	Х
Study Exit Survey									X

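### The scheduled adverse event assessments are tied to no form: the diary asks about side effects only after resolution and the exit form not at all, so some events may rest on unprompted reporting

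*Combined protocol and SAP*

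**What the plan says.** The schedule of activities (section 6.2) has a row labelled "AE Assessment". It is marked at event start and at 15, 30 and 60 minutes for Events 1, 2 and 3, and again at study exit. The same schedule marks the headache diary at event start and at 60 minutes.

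Section 6.1 times the diary differently: "Once the participant's symptoms resolve, the participant will complete the headache diary". It adds that participants will be instructed, after taking the product, to complete an Adverse Event form for side effects they experience. That instruction carries no condition on resolution. Only the first episode is compulsory: "After the first headache episode, the participant will be asked to complete the same process for another 2 headache episodes; however, these are not required".

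The diary (Appendix E) provides a pain scale at each of the four time points. A closing block, headed for completion where applicable once the headache has resolved, includes "Did your symptoms resolve completely with the test product? Yes No If yes, time of complete symptom resolution", then other medication taken, and last "Did you experience any side effects after taking the test product? (Y/N) If yes, Please fill out the Adverse Event form".

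The exit form (Appendix F) asks about overall experience, perceived help and avoidance of other medication, and includes "How likely are you to recommend the test product to your friends or family members". None of its legible items concerns side effects. The Adverse Event form (Appendix G) is separate and opens with its own yes/no question on side effects.

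**The concern.** The schedule describes repeated AE assessment. The visible forms ask once per headache, at a point defined by the end of that headache, and do not ask at exit. Everything else depends on the participant deciding that something was a side effect and opening the Adverse Event form.

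This matters more here than in a clinic-based trial. All AEs are self-reported (section 6.4), there are no clinic visits (section 4), and there is no medical review of symptoms (section 11). The contact planned at 30 days (section 6.5) is about headache episodes and continuation, not safety. Headache is itself on the list of anticipated AEs (section 6.4.1), so a persisting or worsening headache is a case where the diary's question may not be reached. The AE summary is listed with the secondary endpoints (synopsis and section 3), and section 10 foresees promotional use of the results. An undercount would favour the product.

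**Working it through.** The protocol prints no total for the AE row, so I counted its marks. With k episodes, marks = 4k + 1 (four per event plus exit). The diary has one side-effect item per episode, so k items. The exit form has none that is legible.

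- One episode: 4 × 1 + 1 = 5 marks; 1 diary item.
- Two episodes: 4 × 2 + 1 = 9 marks; 2 diary items.
- Three episodes: 4 × 3 + 1 = 13 marks; 3 diary items.

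Schedule and forms side by side:

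| Moment | AE mark in 6.2 | Side-effect item visible in the appendices |
|---|---|---|
| Onset | yes | none (headache description, pain scale) |
| 15, 30, 60 minutes | yes | none (pain scale only) |
| After the headache has resolved | no | diary yes/no, last item |
| Study exit | yes | none legible |
| Any time after a dose | no | Appendix G, if the participant starts it |

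Three cases, followed through the forms as written:

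1. The headache resolves, with the product or with other medication, and the side effect occurs before the diary is finished. The diary asks. Nothing is lost by design.
2. The headache does not end. Read literally, the heading of the closing block is never met and neither is the diary timing in section 6.1. The diary row in section 6.2, at 60 minutes, points the other way. Under the literal reading only Appendix G remains. The case is not remote to the planners: one baseline question (Appendix D) is "How long do your Headaches usually last without medication? (30 min-1hour, 1-2 hour, >2 hours, does not resolve".
3. The event begins after the diary is closed. That diary has no further item, a second or third diary may never be opened, and the exit form does not ask. Section 6.1 exits a one-episode participant at day 60, so this interval can be long. Again only Appendix G remains.

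In cases 2 and 3 the data have two indistinguishable states. An absent Adverse Event form means either that nothing happened or that something happened and no form was opened. A required yes/no item separates them, because a recorded No differs from a blank.

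**The case against.** The strongest reply is that the protocol has a dedicated AE instrument. Appendix G asks its own yes/no question, and section 6.1 directs participants to it after dosing without regard to resolution. The documents do not say when the portal presents it, so it could serve every mark in the schedule. This stands against the reading that participants with unresolved headaches may never be asked; the documents do not establish that. It does not close the gap, because both section 6.1 and the diary route participants to Appendix G only if they have already noticed a side effect.

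A reader might also infer that the diary question depends on a good efficacy result. The documents do not support this. The block accepts No for complete resolution with the product, records up to three other medications, and asks again about resolution with them. It is built to include product failures. The condition is at most that the headache ended by some means.

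Nor does 13 marks against 3 diary items mean ten lost assessments. One diary answer covers the whole period since dosing, Appendix G asks how soon the effect began, and three of the 13 marks fall at event start, where little can yet have happened.

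Finally, a coordinator may chase forms (section 6.3), and completed forms are reviewed before the gift card is sent (section 6.1). Those checks can find a blank required form. They cannot find an Adverse Event form that is due only if the participant had a side effect.

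**Conclusion.** The point holds as a mismatch between schedule, procedures and forms, with a possible effect on AE capture. The marks in section 6.2 (5 to 13 per treated participant) are linked to no form. The exit mark has no legible item behind it. Sections 6.1 and 6.2 disagree on when the diary is completed. For headaches that do not end and for late events, ascertainment may rest on unprompted self-report, and the AE summary may undercount.

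The size cannot be given. It depends on the share of episodes without resolution, the AE risk in them and the rate of unprompted reporting, none of which the documents state. A reader might infer a large loss. With purely assumed values of 20% unresolved, AE risk 10% in those and 5% otherwise, the true rate is 0.2 × 10% + 0.8 × 5% = 6.0%. If every event in a resolved episode is reported and none in an unresolved one, 0.8 × 5% = 4.0% is captured, a loss of one third. If unprompted reporting is complete, the loss is zero. The one-third figure ignores the section 6.1 instruction and is a worst case under invented inputs, not an estimate.

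Two limits apply. The product insert (Appendix H) breaks off in the available copy, exit item 5 is garbled, and the portal's prompts are not shown, so a further AE prompt cannot be excluded. Even so, the mismatch among the visible parts would remain to be reconciled.

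**What to change.** 1. In Appendix E, put the side-effect yes/no item directly under the 60-minute pain scale and make it required whether or not the headache has resolved. Keep the later item for effects that arise afterwards.
2. In Appendix F, add a required yes/no item on any new or worse health problem since the first dose, opening Appendix G if the answer is yes. The gift card follows receipt of the exit survey, so this form is a natural last check.
3. Reconcile the AE and diary rows of section 6.2 with section 6.1 and the forms, and name the form that serves each AE mark.

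The cost is two tick-box items on existing electronic forms and a small amendment. The downside is a few extra seconds per form and more minor AE reports to review.
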